6.5.3.1 Ophthalmological Examination

Ophthalmological examination will be performed at screening (within 28 days prior to futibatinib administration on Day 1 of Cycle 1), 4-6 weeks after starting treatment with futibatinib, and as indicated if symptoms or signs of mineral deposits. Ophthalmological examination encompasses external ocular examination, slit lamp biomicroscopy and dilated ophthalmoscopy. The results of each test will be summarized by scheduled time point. All ophthalmological examination results will be listed in by-patient listing.

5.5.4. Vital Signs

Vital sign measurements include systolic blood pressure, diastolic blood pressure, heart rate, respiration rate, and body temperature. Each vital sign parameter will be summarized with descriptive statistics by scheduled time point. Change from baseline will be summarized in a similar manner.

Weight at each scheduled time point and change from baseline will be summarized with descriptive statistics by scheduled time point. Weight will be displayed in kilograms. Height, collected only at baseline, will be displayed in centimeters. Body temperature will be displayed in Celsius.

All vital sign data will be presented in by-patient listings.

5.5.5. Electrocardiograms

ECG measurements include HR, RR interval, QT interval, its Fridericia's correction, and proportion of clinically abnormal findings. QTcF (Fridericia's correction) is calculated as $QT/RR^{0.33}$. These ECG parameters will be summarized. Abnormal and abnormal plus clinically significant ECG findings will also be summarized.

All ECG data will be presented in by-patient listings.

5.5.6. Physical Examination

The physical examination will be performed during screening period, on day 1 of each cycle of treatment period, at the End of Treatment, and at safety follow-up.

The physical examination data will be presented in by-patient listing.

5.5.7. ECOG Performance Status

The ECOG performance status score will be obtained during screening period, on day 1 of each cycle of treatment period, at the End of Treatment, and at safety follow-up. The ECOG performance status scores and the grades from 0 to 5 are described in Table 12:

Table 12. Grade Categories of Eastern Cooperative Oncology Group Score

GRADE	ECOG
0	Fully active, able to carry on all pre-disease performance without restriction
1	Restricted in physically strenuous activity but ambulatory and able to carry out work of a light or sedentary nature, eg, light house work, office work
2	Ambulatory and capable of all self-care but unable to carry out any work activities; up and about more than 50% of waking hours
3	Capable of only limited self-care, confined to bed or chair more than 50% of waking hours
4	Completely disabled; cannot carry on any self-care. Totally confined to bed or chair
5	Dead

The ECOG performance status score will be summarized with descriptive statistics by scheduled time point. A shift table will be presented to display the shift from baseline grade to the worst post-baseline grade.

5.5.8. Pregnancy Test

If the patient is female and of child bearing potential, a test will be performed during screening period and at the End of Treatment. Pregnancy test result will be presented in by-patient listing.

CCI

CCI

CCI

CCI

5.8. Interim Analyses

The first interim analysis of safety will be performed after the first 6 patients in the safety lead-in period have completed cycle 1 of treatment. The second interim analysis of safety will be performed after a total of 10 patients (including the initial 6 patients enrolled in the safety lead-in period) have completed cycle 1 of treatment.

Additional ad-hoc interim analysis for safety or efficacy may be performed as deemed as appropriate.

5.9. Other Analyses

Assessments were not completed or missed due to COVID-19 will be listed per visit.

6. DEFINITIONS AND CONVENTIONS FOR DATA HANDLING

6.1. Baseline Period

Baseline evaluations or events will be defined as evaluations or events that occur before the date and time of the first dose of study drug.

If the onset time of event or evaluation time or dosing time is missing or not collected, the following definitions will apply:

- Pre-treatment AEs will be defined as AEs with an onset date prior to but not including the day of the first dose of study drug
- Baseline evaluations (laboratory tests, ECOG performance status and vital signs) will be defined as evaluations with a date on or prior to the day of first dose of study drug (for ECG, assessments on the day of first dose of study drug will not be included in baseline evaluation)

If there are multiple valid assessments, the assessment that is closest to day (and time if collected) of the first dose of study drug will be used as the baseline in the analyses. If multiple assessments are collected on the same date (and time, if collected), the assessment with the latest database entry date (and time, if collected) will be considered as baseline.

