4.2. Exclusion Criteria

A patient must not meet any of the following exclusion criteria to be eligible for participation in this study; waivers will not be granted for any of the eligibility criteria.

1. Have received prior therapy with anti-PD-1, anti-PD-L1/L2 agent.
2. Have received prior FGFR inhibitor treatment including futibatinib
3. History and/or current evidence of any of the following disorders:
 - a. Non-tumor related alteration of the calcium-phosphorus homeostasis that is considered clinically significant in the opinion of the Investigator

- b. Ectopic mineralization/calcification, including but not limited to soft tissue, kidneys, intestine, or myocardia and lung, considered clinically significant in the opinion of the Investigator
- c. Retinal or corneal disorder confirmed by retinal/corneal examination and considered clinically significant in the opinion of the Investigator.

4. Corrected QT interval using Fridericia's formula (QTcF) >470 msec. Patients with an atrioventricular pacemaker or other condition (for example, right bundle branch block) that renders the QT measurement invalid are an exception and the criterion does not apply.

5. Has received major surgery within the previous 4 weeks.

6. Has received any non-investigational anticancer therapy within the previous 3 weeks (mitomycin within the previous 5 weeks).

7. Is currently participating in a study of an investigational agent/device, or has participated in a study of an investigational agent or used an investigational device within 4 weeks prior to the first dose of study treatment.

8. Has received a live vaccine within 30 days prior to the first dose of study drug. Examples of live vaccines include, but are not limited to, the following: measles, mumps, rubella, varicella/zoster (chicken pox), yellow fever, rabies, *Bacillus Calmette–Guérin* (BCG), and typhoid vaccine. Seasonal influenza vaccines for injection are generally killed virus vaccines and are allowed; however, intranasal influenza vaccines (e.g., FluMist®) are live attenuated vaccines and are not allowed.

9. A serious illness or medical condition(s) including, but not limited to, the following:

- a. Has an active infection requiring systemic therapy.
- b. Myocardial infarction, severe/unstable angina, or symptomatic congestive heart failure within the previous 6 months
- c. History or current evidence of uncontrolled ventricular arrhythmia

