6. STUDY ASSESSMENTS

The Schedule of Events ([Table 1](#) and [Table 2](#)) summarizes the frequency and timing of all applicable study assessments, including allowable windows for study visits and assessments / procedures. Written informed consent must be provided before any study-related procedures are performed. Any AEs directly associated with a screening procedure should be reported as described in [Section 9.1](#).

Assessment	Details
Review of inclusion/exclusion criteria	See Sections 4.1 and 4.2 . Eligibility must be confirmed prior to first dose of study therapy.
Demographics/medical history	Sex, age, clinical diagnosis, date and method of diagnosis, prior cancer therapy, relevant medical history (past and concurrent).
Baseline signs and symptoms	Signs and symptoms occurring after signing of ICF but before administration of first dose of futibatinib.
Physical examination, Height and body weight	Height is collected for the purpose of BMI calculations at baseline only.
Vital signs	Pulse rate, systolic and diastolic blood pressure, body temperature, and respiration rate. Any abnormal reading should be repeatedly immediately.
ECOG performance status	See Appendix A .
12-lead ECG	Single, resting, semirecumbent 12-lead electrocardiogram (ECG) will be performed locally. Data collection includes RR interval (heart rate), QT interval, QTcF interval and abnormal findings; the Investigator is responsible for interpreting and measuring ECG data.
Hematology	Red blood cell count, hemoglobin, hematocrit, platelets, white blood cell count with differential, neutrophils (ANC), lymphocytes, monocytes, eosinophils, basophils
Chemistry (serum or plasma)	AST, ALT, ALP, bicarbonate, total bilirubin, direct bilirubin, albumin, lactate dehydrogenase, inorganic phosphorus, triglyceride, total cholesterol, creatinine, urea or blood urea nitrogen, bicarbonate, sodium, potassium, chloride, calcium (corrected value), magnesium, blood glucose, uric acid For a calculated creatinine clearance (Ccr) value, use the Cockcroft-Gault formula: Male Ccr (mL/min) = Body wt (kg)×(140-age)[72×serum creatinine (mg/dL)] Female Ccr (mL/min) = male Ccr×0.85
Thyroid function tests	Triiodothyronine (T3) or free triiodothyronine (FT3), free thyroxine (FT4), and thyroid stimulating hormone (TSH).
Coagulation	Prothrombin time-international normalized ratio, activated partial thromboplastin time, fibrinogen

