Please note: at each safety interim analysis, the combination of futibatinib and pembrolizumab will be considered intolerable if the incidence of unacceptable toxicity including dose-limiting toxicity (as defined in Section 5.2 “Definition of Dose-Limiting Toxicity” of the protocol) is $\geq 33\%$. If the combination is determined to be intolerable, the study may continue with a reduced dose of futibatinib (16 mg QD) if medically appropriate in the opinion of the investigator and Sponsor.

Of note, the 6 patients initially enrolled in the safety lead-in period will also be assigned to the respective cohort based on *FGFR* alteration, such that each cohort will contain a minimum of 20 and a maximum of 26 patients.

The detailed study schedule is shown in Table 1.

Table 1. Schedule of Events

Evaluations on Day 1 (D1) of a cycle should be performed within 24 hours prior to dosing, unless otherwise noted. Procedures already performed during the screening period within 72 hours prior to dosing do not need to be repeated on Cycle 1D1 (C1D1). The End of Treatment (EOT) visit must be performed 0-7 days after a decision is made to discontinue study treatment (for patients who discontinue at a planned study visit, that visit may be considered the EOT visit if all assessments required at EOT are performed).

Evaluation	Screening (Within 28 days of 1 st dose)	Treatment Period (1 cycle =21 days)					Safety Follow-up	Survival Follow-up Period (every 12±2 weeks)	Notes			
		Cycle 1		Cycle ≥2								
		D1 (-1 day)	D8 (-1 day)	D15 (-1 day)	D1 (-1 day)	End of Cycle (±7days)						
Written informed consent	X									Written informed consent will be obtained prior to any study-related assessments or procedures.		
Review eligibility criteria	X											
Demographics/medical history	X											
Review of baseline signs and symptoms	X											
Prior & concomitant medications, AE assessments							►			Collect from the time main informed consent is signed through 90 days after administration of the last dose of study therapy or until the start of new anticancer therapy, whichever is earlier.		
Physical examination	X	X			X		X	X		Within 24 hours prior to dosing.		
Vital signs	X	X			X		X	X		Heart rate, blood pressure, body temperature, and respiration rate.		
Height and Weight	X	X			X		X	X		Height at screening only.		
ECOG performance status	X	X			X		X	X		Within 24 hours prior to dosing.		
12-Lead electrocardiogram		X			X		X	X				

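### When an ECG or dosing time is missing, SAP 6.1 bars a same-day Cycle 1 Day 1 ECG from baseline, although it is the only pre-dose ECG on the schedule

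*SAP*

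**What the plan says.** SAP 6.1 starts from a general rule: "Baseline evaluations or events will be defined as evaluations or events that occur before the date and time of the first dose of study drug". It then adds a fallback: "If the onset time of event or evaluation time or dosing time is missing or not collected, the following definitions will apply". Under the fallback, laboratory tests, ECOG performance status and vital signs dated on or before the first dosing day are baseline. ECG is the stated exception: "for ECG, assessments on the day of first dose of study drug will not be included in baseline evaluation".

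The row "12-Lead electrocardiogram" appears in SAP Table 1 and, with the same pattern, in Protocol Table 1. The screening cell is blank. The first mark is at Cycle 1 Day 1, followed by Day 1 of later cycles, end of treatment and safety follow-up. The SAP table's header gives the timing: "Evaluations on Day 1 (D1) of a cycle should be performed within 24 hours prior to dosing, unless otherwise noted". The Day 1 column carries a window of minus one day. The header also lets a procedure done in screening within 72 hours of dosing stand in for its Cycle 1 Day 1 repeat.

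SAP Table 2 ends the baseline/screening period at the day and time of first dose. It starts the on-treatment period on the date of first dose and makes that period the default basis for safety summaries. SAP 5.5.5 summarizes ECG parameters and abnormal findings and lists all ECG data by patient.

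On eligibility, exclusion criterion 4 in Protocol 4.2 uses a corrected QT limit, "formula (QTcF) >470 msec". Protocol Section 6 adds "Eligibility must be confirmed prior to first dose of study therapy".

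**The concern.** Excluding an untimed same-day ECG from baseline does no harm where a screening ECG can take its place, but here none is scheduled. Laboratory tests, ECOG status and vital signs all have scheduled screening values and also keep their Day 1 records. The ECG has no scheduled screening value and is the assessment whose Day 1 record is set aside, even though the schedule places that recording before dosing.

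What is at stake is how ECG findings are read. The study has no control group, so a patient's own pre-dose tracing is the main reference for later ones. If that tracing is removed from baseline and tabulated with on-treatment recordings, an abnormality present before any study drug could be taken for one that arose under treatment.

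**Working it through.** The plan gives no figure to reproduce. The check sets the fallback rule against the schedule and the study periods.

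**Step 1: scheduled pre-dose ECGs.** Screening contributes 0 (blank cell in both tables) and Cycle 1 Day 1 contributes 1 (pre-dose by the table header), so 0 + 1 = 1 per patient. The blank cell is the same in both documents, and the adjacent ECOG row is marked at both screening and Day 1, so a text-extraction fault is unlikely.

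**Step 2: when that one ECG survives as baseline under SAP 6.1.**

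| Situation | Rule that applies | Usable baseline ECGs |
|---|---|---|
| ECG and dosing times both recorded, ECG before dose | General rule | 1 |
| ECG dated the day before dosing (within the Day 1 window), time missing | Fallback; ECG not on the dosing day | 1 |
| ECG dated on the dosing day, either time missing, another ECG on an earlier day | Fallback; the earlier ECG is used | 1 |
| ECG dated on the dosing day, either time missing, no other pre-dose ECG | Fallback; ECG excluded | 0 |

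Only the last row loses the baseline. It needs all three conditions together: same date, a missing time, and no other pre-dose tracing. A missing dosing time is enough on its own, even if the ECG time was recorded.

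**Step 3: where the excluded ECG goes.** SAP 6.1 says only that it is not baseline. SAP 6.2 has the title of a post-baseline section but classifies adverse events only. The placement therefore has to be inferred from SAP Table 2. On the first dosing day its two periods overlap: baseline runs up to the dosing time, and on-treatment begins with the date. Once 6.1 has removed the ECG from baseline, only the on-treatment period is left. That period is the default basis for the safety summaries, which include those in 5.5.5.

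**Step 4: which outputs are touched.** SAP 5.5.5 plans summaries of ECG parameters and of abnormal findings. It specifies no change from baseline and no shift table. SAP 5.5.4, by contrast, does specify change from baseline for vital signs. The protocol's own safety section plans only a by-patient listing of ECG findings. The exposure is therefore the baseline entry of the ECG summary and the count of abnormal findings attributed to the on-treatment period.

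**Step 5: how often.** Protocol Section 6 names RR, QT, QTcF and abnormal findings as the ECG data and does not mention a clock time. That makes missing times plausible but does not establish them, because the case report form is not among the documents. Against planned enrolment of about 46, the number affected can lie anywhere from 0 to about 46, and nothing in the documents narrows this range.

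**The case against.** The strongest case on the other side is that the general rule already covers the normal situation. With times recorded, a pre-dose Cycle 1 Day 1 ECG is baseline. The fallback needs a missing time, and the ECG content listed in Protocol Section 6 is not shown to be a complete list of collected fields. Declining to assume that an untimed same-day ECG preceded dosing is also a cautious convention that can be defended. All of this stands as a limit on frequency. It does not explain why ECG is treated more strictly than the other Day 1 evaluations when the same header places them all before dosing.

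The QTcF exclusion also implies that some ECG exists before dosing. If sites take it on an earlier day, the baseline survives. This is fair, but such an ECG would be unscheduled, and the Cycle 1 Day 1 tracing could itself be the one used: Protocol 3.2.1 runs screening up to the date of first dose.

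Three stronger readings are tempting, and the documents do not support them:

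- **That every patient loses the baseline ECG.** The loss needs the three conditions in the last row of the table.
- **That QTcF change from baseline can no longer be analysed as planned.** Neither document plans a change-from-baseline or shift analysis for ECG. The recordings also stay visible in the by-patient listings.
- **That the SAP states these ECGs are post-baseline.** It does not; the placement is an inference from Table 2.

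**Conclusion.** The fallback in SAP 6.1 conflicts with the schedule it is applied to: it sets aside the only scheduled pre-dose ECG whenever that ECG is dated on the dosing day and a time is missing. For a patient with no other pre-dose tracing, the result is 0 baseline ECGs instead of 1. One pre-dose recording is then placed, by inference, among the on-treatment ECG summaries.

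The number of such patients is unknown. The primary endpoint and the interim tolerability rule do not use the ECG baseline definition. The effect is confined to how ECG parameters and abnormal findings are presented and read. The point is worth correcting because the conflict is plain in the text and the change is small.

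The conclusion assumes that the Cycle 1 Day 1 ECG is done before dosing as the header requires, and that Table 2 governs ECG data as it does other safety summaries.

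The mismatch between the QTcF criterion and the blank screening cell is real but separate. A reader might infer that eligibility cannot be checked. The documents do not support that, since a pre-dose Cycle 1 Day 1 ECG could serve. What is missing is an entry on the schedule showing which ECG is meant.

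**What to change.** In SAP 6.1, replace the ECG exception: when an ECG or dosing time is missing, treat the scheduled Cycle 1 Day 1 ECG as baseline, as for laboratory tests, ECOG status and vital signs, unless it is documented as post-dose. In SAP 5.5.5, state that baseline is shown separately from post-baseline in the ECG summaries.

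Separately, reconcile exclusion criterion 4 with the ECG row of Table 1 in both documents, so that the ECG used for eligibility appears on the schedule.

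The cost is a sentence in each of two SAP sections and an aligned entry in the schedule tables. The analysis change needs no new data. Its small downside is that an untimed ECG actually taken after dosing could be counted as baseline; collecting ECG and dosing times would remove that risk.

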6.2. Post-Baseline Period

To allow differentiation as to which study period an Adverse Event occurred, three categories are defined based upon onset date. Adverse Events that had onset dates prior to the first dose of study drug are considered "prior". Adverse events with onset dates on or after the first dose of study drug and within 30 days following the last dose of study drug are considered "**on-treatment**" or equivalently "**treatment emergent**". Events with onset dates more than 30 days after the last dose of study drug are considered as "post-treatment". No "subtracting rule" will be applied when an AE occurs both pre-treatment and post-treatment with the same preferred term and grade. AE summary tables will be based on on-treatment AEs only. Adverse events with onset dates prior to the first dose of study drug as well as those after the last dose of study drug +30 days will be identified in the data listings.

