9. SAFETY EVALUATIONS

9.1. Adverse Events

An AE is defined as any untoward medical occurrence in a clinical study patient and does not necessarily have a causal relationship with the study drug. An AE can therefore be any unfavorable and unintended sign (including an abnormal finding), symptom, or disease temporally associated with the use of a study drug, whether or not related to the study drug. This includes any occurrence that is new in onset or aggravated in severity or frequency from the baseline condition, or abnormal results of diagnostic procedures, including laboratory test abnormalities.

All AEs will be collected from the time the ICF is signed through 30 days after the last dose of any study therapy (safety follow-up) or until the start of new antitumor therapy, whichever is earlier; SAEs will be collected through 90 days after the last dose of any study therapy. For all AEs that occur between signing ICF and first dose of study therapy, there is no need to record those that are unrelated unless it is mandatory by local regulations. All AEs will be documented in the eCRF. Any untoward medical event that occurs after the safety follow-up is not considered an AE, unless the Investigator considers that the AE is related to the study drug. Serious AEs related to study therapy will be collected through the survival follow-up.

Signs and symptoms of a pre existing disease should not be considered an AE, but should rather be considered baseline signs and symptoms. Clinically significant worsening of pre existing signs and symptoms is considered an AE.

For definitions and reporting of pregnancies, overdoses, and medication errors, refer to [Section 9.5](#).

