5.5.2.2. Adverse Events

AE is any untoward medical condition that occurs in patients while participating in this clinical study. Adverse events will be coded according to the MedDRA (the most up-to-date version at the time of analysis) terminology and the severity of the toxicities will be graded according to NCI CTCAE (Version 5.0), where applicable.

An on-treatment AE is defined as an AE that is starting or worsening at the time of or after the first dose of study drug administration and within 30 days after the last dose of study drug, and do not necessarily have a causal relationship to the use of the study drug. All AEs captured in the database will be listed; however, only on-treatment AEs will be summarized.

The following AE summary tables will be generated:

- 1) Summary of AEs with the number and percentage of patients reporting AEs, serious AEs, grade ≥ 3 AEs, AEs leading to study drug discontinuation, interruption and dose reduction, and AEs with outcome of deaths.
- 2) Summary of treatment-related AEs with the number and percentage of patients reporting AEs, serious AEs, grade ≥ 3 AEs, AEs leading to study drug discontinuation, interruption and dose reduction, and AEs with outcome of deaths.
- 3) Summary of AEs by worst CTCAE Grade (grade 1, 2, 3, 4, 5, any grade, Grade ≥ 3) presented by System Organ Class (SOC) and Preferred Term (PT).
- 4) Summary of treatment-related AEs by worst CTCAE grade (Grade 1, 2, 3, 4, 5, any grade, Grade ≥ 3) presented by SOC and PT.
- 5) Summary of AEs leading to death by SOC and PT.
- 6) Summary of the most common AEs ($\geq 10\%$ incidence) and median time to first AE by SOC and PT.

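### SAP 5.5.2.2 counts an adverse event that worsens after first dose as on-treatment, but SAP 6.2 goes by onset date alone, so a pre-dose AE record that worsens on drug is tabulated under one rule and only listed under the other

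*SAP*

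**What the plan says.** SAP 5.5.2.2 gives the definition used for reporting: "An on-treatment AE is defined as an AE that is starting or worsening at the time of or after the first dose" of study drug, up to 30 days after the last dose. It then says what follows from it: "All AEs captured in the database will be listed; however, only on-treatment AEs will be summarized".

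SAP 6.2 defines the same term again and equates it with treatment emergent. Here "three categories are defined based upon onset date". The on-treatment category is "Adverse events with onset dates on or after the first dose of study drug and within 30 days following the last dose of study drug". For the earlier period, "Adverse Events that had onset dates prior to the first dose of study drug are considered" prior. Events starting more than 30 days after the last dose are post-treatment. The section repeats that the AE summary tables use on-treatment events only and leaves the other categories to the listings. It has no clause on worsening.

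SAP 6.1, for cases where an event or dosing time is missing or was not collected, also uses onset alone: "Pre-treatment AEs will be defined as AEs with an onset date prior to but not including the day of the first dose" of study drug.

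Protocol 9.1 agrees with 5.5.2.2. Its AE definition covers anything "new in onset or aggravated in severity or frequency from the baseline condition". The protocol synopsis rests the safety assessment on treatment-emergent AEs, but the protocol gives no working definition of that term, so the SAP has to supply it.

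**The concern.** One term decides which events enter the AE, SAE, AESI, discontinuation and Grade 3 or higher tables, and the SAP gives it two meanings. Two programmers, each following a different section, could produce different counts from the same data. The difference falls on events that began before treatment and got worse on it. A safety summary should show that kind of event, and the protocol's own AE definition includes it.

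**Working it through.** The SAP states no figure to reproduce. The check sets the two rules side by side on four kinds of record. On drug means from first dose through 30 days after last dose.

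| AE record | Under SAP 5.5.2.2 | Under SAP 6.2 |
|---|---|---|
| Onset on drug | On-treatment, summarized | On-treatment, summarized |
| Onset before first dose, no worsening | Not on-treatment, listed | Prior, listed |
| Onset before first dose at Grade 1; the same record reaches Grade 3 on drug | On-treatment, summarized, including Grade 3 or higher | Prior, listed only |
| As above, but the worsening is a new record with its own on-drug onset date | New record summarized | New record summarized |

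Only the third row gives opposite answers.

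**Direction.** Let S be the records with onset on drug and W the records with pre-dose onset that worsen on drug. Section 5.5.2.2 selects S plus W, and section 6.2 selects S. The 6.2 set is always contained in the 5.5.2.2 set, so following 6.2 can lower a count or leave it unchanged, but never raise it.

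**Does other text settle it?**
- The statement in 6.2 that no subtracting rule applies concerns an event present both before and after treatment with the same preferred term and grade. It does not reclassify a single record that changes grade.
- SAP 6.7 treats a completely missing onset date as on-treatment and handles partial dates. It does not address a known pre-dose onset.
- SAP 6.5 mentions pre-treatment AEs and baseline grades by preferred term, so the SAP expects such records to exist, but it does not say how they are classified.
- SAP 8 reports no change from the planned analyses, and nothing ranks section 5 over section 6 or the reverse.

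**Which records can fall in the third row?** Protocol 6 files signs and symptoms between consent and first dose as baseline. Protocol 9.1 makes clinically significant worsening of pre-existing signs and symptoms an AE, and does not require unrelated pre-dose AEs to be recorded unless local regulations do. That leaves AEs tied to screening procedures (Protocol 6), SAEs after consent (Protocol 9.4.2) and AEs recorded under local rules, where these persist and then worsen within the same record.

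**Size per patient.** SAP 3.3 puts each cohort at 20 to 26 patients. One patient is 1/26 = 3.8 percentage points or 1/20 = 5.0 percentage points. A patient counts once per category, so the reported rate moves by this amount only if the omitted event was that patient's only AE in the category.

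**The case against.** The strongest reply is that the third row may be nearly empty. A reader might infer that the trial will systematically miss worsening renal impairment, hearing loss, neuropathy or anemia, because inclusion criteria 2 and 7 admit patients with these conditions. The documents do not support that. Under Protocol 9.1 a pre-existing condition is baseline and its worsening is the AE, so onset falls on drug and both SAP rules count it.

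The SAP's algorithms also fit separately dated records. Table 13 starts Grade 3-5 resolution from the earliest Grade 3-5 record within a cluster that may hold lower grades, and 5.5.2.7 collapses contiguous occurrences of the same preferred term. If sites open a new record at each worsening, the rules agree. This is only suggestive: Protocol 9.2.1 leaves recording to eCRF guidelines that are not among the documents.

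Nor do the events vanish. All AEs are listed, laboratory worsening appears in the shift tables (SAP 5.5.3), and reasons for dose interruption, reduction and discontinuation are summarized (SAP 5.5.1.2). The 6.1 bullet applies only when times are missing or not collected, so it is not a second general rule.

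All of this limits the reach of the point. None of it removes the conflict between 5.5.2.2 and 6.2 for a single record that worsens.

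**Conclusion.** The SAP is wrong as written on this point: it contradicts itself on which AEs are on-treatment. The severity is minor. The effect needs an AE recorded before first dose, worsening on drug within the same record, and programming that follows 6.2. If all three hold, the event is listed but not summarized, and the error can only be an under-count. The shift is 3.8 to 5.0 points per affected patient, and zero for any category in which that patient has another AE. Hyperphosphatemia is the most frequent treatment-related event on futibatinib (Protocol 1.3.2), so an any-AE rate could well stay unchanged.

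A reader might go on to infer a cohort-wide shortfall, for example 2/20 = 10 points. The documents give no number of affected patients and do not exclude zero, so no such figure is supported. They also do not say that section 6 governs the programming, so under-counting is a possible result of the conflict and not a certain one.

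**What to change.** In SAP 6.2, adopt the 5.5.2.2 definition: an AE with onset before first dose that worsens in grade from first dose through 30 days after last dose is on-treatment, dated from the worsening and shown at the worsened grade. Keep the prior category for pre-dose AEs that do not worsen. Make the same change to the pre-treatment AE bullet in 6.1 so that the three places agree.

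The SAP should also say how worsening is recorded. If one record carries a single onset date and grade, the date of worsening cannot be derived from it, and a new record at the grade increase is needed.

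The cost is a few lines of SAP text and one derivation. If sites already open new records at worsening, no result changes. Otherwise reported AE rates may be slightly higher.
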